#### 4. Ethics in clinical research

Clinical research will follow the World Medical Congress ' Helsinki Declaration ' and other relevant provisions. Before the study began, the clinical study was carried out after the ethics committee approved the test plan. Before each subject is selected for this study, the researcher has the responsibility to fully and comprehensively introduce the purpose, procedure and possible risks of this study to the subjects or their agents, and to sign a written informed consent form. The subjects should be informed that they have the right to withdraw from the study at any time. Informed consent should be retained as a clinical research document for review. The personal privacy and data confidentiality of the subjects will be protected during the study.

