## Abstract

Object name	Analysis of integrated clinical, laboratory and prognostic data of neonates with necrotizing enterocolitis
Goal of study	This retrospective cohort study aims to enroll patients with necrotizing enterocolitis (NEC) from July 1, 2017 to December 31, 2022, conduct a comprehensive analysis of their clinical characteristics, metabolic indicators, laboratory parameters, prognosis, and outcomes, and identify indicators that may predict the progression of neonatal NEC and its associated mortality.
Research design	Retrospective cohort study
Research period	July 1, 2024 to June 30, 2025
Leading unit	Guangzhou Women and Children's Medical Center
Research Consultant	[name]; [name]
Research object	Neonates with necrotizing enterocolitis (NEC) from July 1, 2017 to December 31, 2022, conduct a comprehensive analysis of their clinical characteristics, metabolic indicators, laboratory parameters, prognosis, and outcomes.
Inclusion criteria	(1) Diagnosis of NEC
Excluded criteria	Data that meets any of the following conditions need to be eliminated: (1) Congenital gastrointestinal malformations (e.g., intestinal atresia, Hirschsprung's disease) or spontaneous intestinal perforation; (2) Hereditary metabolic disorders; (3) refusal of participation.
Sample size	220 newborns who suffered from necrotizing enterocolitis between

	July 1, 2017 to December 31, 2022
Data collection	Data collection was performed via structured extraction from electronic medical records. The following variables were systematically retrieved: (1) Neonatal medical history, including sex, gestational age, birth weight, and history of birth asphyxia (e.g., Apgar scores); (2) Maternal medical history, particularly mode of delivery, chorioamnionitis, and premature rupture of membranes; (3) NEC-related clinical parameters: Bell's staging, clinical manifestations (abdominal distension, bloody stools, pneumoperitoneum), complications (patent ductus arteriosus [PDA], sepsis, shock), therapeutic interventions (mechanical ventilation, surgical treatment), and mortality; (4) CBC parameters, lactate levels, and parameters required for calculating the nSOFA score at the onset of NEC.

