## 3. Research scheme and technical route

### 3.1 Research Design

The principal investigator (PI) and project leader of this study are [name], chief physician of pediatrics of the Guangzhou Women and Children's Medical Center. In this study, a retrospective analysis was conducted on 220 enrolled neonates with necrotizing enterocolitis (NEC), with data collected from July 1, 2017 to December 31, 2022. Statistical methods including correlation analysis, multivariate logistic regression, mediation analysis, and receiver operating characteristic (ROC) curve analysis were employed to perform mutual analysis of the collected clinical data, laboratory parameters, and prognostic/mortality outcomes. This analysis aimed to identify meaningful biomarkers and establish a predictive model, thereby providing evidence for the pathophysiological mechanisms underlying NEC progression. It is anticipated that this will optimize clinical decision-making for NEC patients and improve the survival rate and quality of life of these neonates.

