### 3.5 Excluded criteria

Data that meets any of the following conditions need to be eliminated:

- (1) Congenital gastrointestinal malformations (e.g., intestinal atresia, Hirschsprung's disease) or spontaneous intestinal perforation;
- (2) Hereditary metabolic disorders;
- (3) Incomplete clinical data or refusal of participation.

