### 3.6 Observation items

- (1). Baseline Characteristics: Neonatal demographics (sex, gestational age, birth weight, small for gestational age [SGA] status), maternal factors (mode of delivery, premature rupture of membranes, chorioamnionitis), neonatal birth history (1-min Apgar score  $\leq 7$ , intrauterine distress), and preterm complications (patent ductus arteriosus [PDA], respiratory distress syndrome [RDS], sepsis, shock), feeding pattern, and requirement for mechanical ventilation.

- (2). Laboratory and Clinical Assessment Indicators: Hepatobiliary function:

Albumin, albumin/globulin ratio, total bile acid; Hematologic and inflammatory parameters: White blood cell (WBC), absolute neutrophil (NEU), lymphocyte (LYM), monocyte (MON), eosinophil (EOS) counts, red blood cell (RBC), platelet (PLT) count, mean platelet volume (MPV), platelet distribution width (PDW), C-reactive protein (CRP), neutrophil-to-lymphocyte ratio (NLR), monocyte-to-lymphocyte ratio (MLR), neutrophil-to-monocyte ratio (NMR), systemic inflammatory index (SII), systemic inflammatory response index (SIRI), aggregate inflammatory systemic index (AISI); Metabolic: Serum lactate, blood glucose; Organ dysfunction assessment: Neonatal Sequential Organ Failure Assessment (nSOFA) score.

(3). Primary Outcome Indicators:

- Occurrence of perforated necrotizing enterocolitis (PNEC);
- In-hospital mortality.

(4). Secondary Outcome Indicators:

- Bell's staging of NEC;
- surgical NEC

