#### 5. Research progress

July 2024 - August 2024: Project pre-planning, standardization of data collection, and training of personnel Training

August 2024 - March 2025: The specific implementation stage of the experiment, collecting case data

March 2025 - June 2025: Writing scientific research papers and project summary reports (1) Organizing research data and conducting statistical analysis; (2) Writing and submitting scientific research papers; (3) Summarizing research results and writing the project summary report.

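### Section 4 requires signed consent before selection in a record review of 2017-2022 infants; if consent differs by vital status, observed mortality and predicted risk are biased

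*Combined protocol and SAP*

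**What the plan says.** Section 3.1 describes the design: "a retrospective analysis was conducted on 220 enrolled neonates with necrotizing enterocolitis (NEC), with data collected from July 1, 2017 to December 31, 2022". The Abstract gives the research period as "July 1, 2024 to June 30, 2025", and Section 5 schedules "August 2024 - March 2025: The specific implementation stage of the experiment, collecting case data". Section 3.3 describes extraction from electronic records and no contact with families.

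Section 4 sets an entry rule of another kind. It reads "Before each subject is selected for this study, the researcher has the responsibility to fully and comprehensively introduce the purpose", along with the procedure and risks, to the subject or the subject's agent, and "to sign a written informed consent form". Participants must also be told that "they have the right to withdraw from the study at any time".

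Section 3.5 lists among the exclusions "Incomplete clinical data or refusal of participation", and the Abstract also excludes refusals. Section 3.6 names "In-hospital mortality" as one of two primary outcomes; the other is perforated NEC (PNEC).

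No section mentions a consent waiver, a rule for infants who died or families who cannot be traced, a count of those approached or refusing, or an analysis that allows for non-consent. Section 3.2 gives 220 as the sample size without saying whether that is before or after refusals.

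**The concern.** The study opens 18 months after the last eligible date and seven years after the first. Under Section 4 as written, each family would be approached after the infant had died or gone home. Parents of an infant who died may be harder to trace, less willing to sign, or occasionally more willing. Any such difference makes entry to the cohort depend on a primary outcome.

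Three things would be at stake:

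- the observed mortality proportion;
- the absolute risks from any prediction model, which Section 3.1 says the study aims to establish in support of clinical decisions;
- the number of deaths available for the mortality analyses.

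Without a count by vital status, a reader could not tell whether reported mortality reflects the disease or reflects who signed.

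**Working it through.** **The plan's own figure.** The only relevant figure is 220. It has no stated inputs (event rate, consent rate or power), so it cannot be reproduced. The check asks what the consent rule would do under stated assumptions.

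**Inputs.** From the documents: n = 220, described as enrolled (Section 3.1), and death as a primary outcome (Section 3.6). Assumed: true mortality p = 25%; consent among survivors cs = 90%; consent among bereaved families cd, varied.

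**Observed mortality** = p·cd / [p·cd + (1 − p)·cs]

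- cd = 90%: 0.225 / (0.225 + 0.675) = 25.0%, no bias.
- cd = 60%: 0.150 / (0.150 + 0.675) = 0.150 / 0.825 = 18.2%.
- cd = 40%: 0.100 / (0.100 + 0.675) = 0.100 / 0.775 = 12.9%.
- Reverse case, cd = 90% and cs = 70%: 0.225 / (0.225 + 0.525) = 30.0%, an upward bias.

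**Deaths among 220 enrolled.** Without bias 220 × 0.25 = 55; at 60% bereaved consent 220 × 0.182 = 40; at 40%, 220 × 0.129 = 28.

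**Against sampling error.** The standard error of a 25% proportion at n = 220 is √(0.25 × 0.75 / 220) = 2.9 points. The drops of 6.8 and 12.1 points are about 2.3 and 4.1 standard errors.

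**Other base rates.** At 90% survivor and 50% bereaved consent, true mortality of 10%, 20% and 30% appears as 5.8%, 12.2% and 19.2%.

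**Predicted risk.** If entry depends on death alone, the logistic intercept moves by ln(cd/cs) and the slopes do not move. The shift is ln(0.6/0.9) = −0.41 or ln(0.4/0.9) = −0.81. An infant with a true risk of 60% (odds 1.5) is given odds of 1.5 × 0.667 = 1.0, a risk of 50%, or 1.5 × 0.444 = 0.667, a risk of 40%.

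**Odds ratios and AUC.** A simulation of 1,000,000 infants used one standardised marker, PNEC and 20% mortality, with entry depending only on death. All effect sizes are assumptions. Moderate effects are log odds ratios for death of 0.7 (marker) and 1.0 (PNEC); stronger effects are 1.0 and 1.5.

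| Consent, survivors/bereaved | Effects on death | Marker OR for death | Marker AUC for death | Marker OR for PNEC | Marker AUC for PNEC |
|---|---|---|---|---|---|
| 100/100 | moderate | 2.00 | 0.706 | 1.82 | 0.659 |
| 90/50 | moderate | 2.01 | 0.707 | 1.77 | 0.650 |
| 80/40 | moderate | 2.01 | 0.706 | 1.76 | 0.648 |
| 100/100 | stronger | 2.72 | 0.765 | 1.81 | 0.658 |
| 90/50 | stronger | 2.73 | 0.766 | 1.72 | 0.641 |
| 80/40 | stronger | 2.71 | 0.765 | 1.70 | 0.638 |

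The death model keeps its odds ratio and AUC. The PNEC AUC falls by about 0.01 to 0.02. Only in the extreme case run, 20% bereaved consent, does the fall reach 0.02 (moderate) to 0.04 (stronger). For scale, with 35% PNEC (77 against 143 infants) and an AUC of 0.71, the Hanley-McNeil standard error is about 0.038.

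**Mediation.** Section 3.7 names no exposure or mediator. Taking lactate to nSOFA as an example, with an assumed standardised slope of 0.50, the slope drifts to 0.49 or 0.48 at 60% or 40% bereaved consent. Its standard error at n = 220 is about 0.059.

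**The case against.** The strongest reply is that Section 4 may be standard trial wording that nobody intended to apply here. Section 3.3 describes record extraction only, Section 5 schedules no step for contacting families, and Section 3.1 already calls the infants enrolled. This stands in part: the documents do not settle whether families were approached. But Section 4 is then wrong about how infants enter, the refusal exclusion has no clear meaning, and both still need correcting.

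A second reply is that the plan's stated performance measure is the ROC curve, which survives selection on death alone, and that no mortality estimate or calibration analysis is specified. The point about ROC is right. It does not protect predicted risk, which matters to the predictive model announced in Section 3.1. It would also fail if consent depended on death and the markers jointly.

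Three stronger readings are tempting, and the documents do not support them:

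- **That entry did depend on outcome and the results are biased downward.** No consent, refusal or tracing rate is given, overall or by vital status. Equal consent gives zero bias, and the direction can reverse.
- **That the PNEC and mediation analyses are materially distorted.** Selection on death does reach them, but apart from the extreme case the drifts are at most about half a standard error.
- **That only 33 or 22 of 55 deaths would remain.** This treats 220 as the total before consent. At the assumed rates, enrolment would then be 220 × 0.825 = 182 or 220 × 0.775 = 171, whereas Section 3.1 describes 220 as enrolled.

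**Conclusion.** The concern holds conditionally. As written, the plan places consent after a known primary outcome, excludes refusals, and gives no waiver and no accounting by vital status. That inconsistency with a retrospective record review is certain from the text; the bias is a possible consequence of it.

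If bereaved families enter less often than others, observed mortality and predicted risk are too low, by about 7 to 12 percentage points for mortality in the scenarios shown. If they enter more often, the error is upward; if equally often, there is none. These sizes rest on assumed values for mortality and consent, and on entry depending on vital status alone. Under that last condition the odds ratios and AUC for death are unaffected, and the PNEC and mediation results are affected little. The point should be fixed, because the exposure falls on a primary outcome and the remedy is cheap whatever the true rates are.

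**What to change.** Reconcile Section 4 with the retrospective design.

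1. **Preferred.** Ask the ethics committee to waive individual consent for de-identified existing records, or state in Section 4 that a waiver was granted. If it is granted, remove refusal as an exclusion from Section 3.5 and the Abstract, so that every otherwise eligible infant enters.
2. **If the committee requires consent.** State how and when it is sought, including for infants who died. Report eligible, untraceable, refused and included counts by vital status. Say whether 220 is the number before or after refusals. Add a sensitivity analysis of mortality and predicted risk, weighting each infant by the inverse probability of inclusion given vital status.

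The weights need only aggregate counts of eligible deaths and survivors. As a check at 60% and 90% consent, 40 deaths and 180 survivors enrolled give 40/0.6 = 66.7 and 180/0.9 = 200, and 66.7/266.7 = 25%, the assumed true value. The text should say that this corrects only for selection on vital status; if consent also depends on severity, bias remains. For that reason, and because differential consent is not shown, weighting belongs in a sensitivity analysis and not in the primary one.

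Cost: one request to the ethics committee and edits to Section 4, Section 3.5 and the Abstract; or one flow table and one additional analysis with inference that respects the weights.

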#### 5. Research progress

July 2024 - August 2024: Project pre-planning, standardization of data collection, and training of personnel Training

August 2024 - March 2025: The specific implementation stage of the experiment, collecting case data

March 2025 - June 2025: Writing scientific research papers and project summary reports (1) Organizing research data and conducting statistical analysis; (2) Writing and submitting scientific research papers; (3) Summarizing research results and writing the project summary report.

